**Figure 2. Study Population Flow**

6. Patients who are eligible after screening will be asked to provide informed consent (study and evaluation interview) and to complete HIPAA B forms. Informed consent will be conducted in-person, whenever possible. If geographic distance prohibits an in-person visit, the patient will be mailed the consent forms and a member of the study team will contact the patient via telephone to conduct the informed consent process. If amenable, the patient will sign the consent form and return it to the study team. Patients will be offered a \$10 incentive for participation, provided at the baseline, 4m and 12 month visits and \$15 at the 6 month visit. Participants may decline payment.

Patients will be assigned a study identifier, a number unrelated to any personal identifying information. Data will be kept on a secured server (see Protocol Application for details). No surveys will be labeled with the subject's name or identifying information. The surveys will be coded with the patient's study identification number.

VA providers may refer their patients to the study.

The research coordinator, research assistant, study social worker and the study nurse may contact and conduct study procedures with patients according to the protocol at both sites.

Prior to the start of the study, all research staff will be trained and will practice the screening and consent process. The training will include the process of fully explaining the study and consent procedures, explaining the possible risks and inconveniences, answering patient questions and assessment of the patient's understanding of the study and consent process.

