Research staff at VA ECHCS will assist PSVAHCS in some aspects of recruitment, follow-up data collection and the process evaluation. The Intervention SW and RN at each site will interact with participants at both sites.

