## IV. Research Methods

### A. Outcome Measure(s):

**Aim 1:** The measures were chosen to reflect domains of the conceptual model (Figure 1) as follows (instrument abbreviations defined below):

- **Antecedents:** Demographics; CHF factors (e.g., left ventricular ejection fraction); COPD factors (e.g., spirometry)
- **Symptom Experience:** GSDS (symptom distress), Symptom assessments
- **Depression:** PHQ
- **Health-Related Quality of Life:** FACT-G (primary outcome measure), QUAL-E, KCCQ-12, CCQ, K-BILD
- **Health Care Utilization:** Hospitalizations
- **Advance care planning communication, documentation:** patient-reported advance care planning communication, advance directive documentation in Electronic medical record review

1. **FACT-G** (primary outcome): The Function Assessment of Chronic Illness Therapy-General is a widely used, valid, reliable (alpha range, 0.88-0.92), and responsive 27 item self-report measure of health-related quality of life that includes domains of physical, social/family, emotional, and functional well-being. Norms for the general population allow FACT-G scores to be measured and compared across study populations. Validity in CHF and COPD has been demonstrated through FACT-G correlations with disease severity.

2. **QUAL-E:** The Quality of Life at the End of Life is a valid and reliable self-report measure of several domains, each scored separately, of quality of life in advanced illness.

3. **GSDS:** The General Symptom Distress Scale is a single item measure of overall symptom distress that is reliable and valid and asks, "In general, how distressing are all of your symptoms to you?" It is rated on 0 ("not at all distressing") to 10 ("extremely distressing") on a numeric rating scale.

4. **PHQ-8:** The Patient Health Questionnaire-8 is an 8-item valid and reliable instrument that provides a continuous measure of depressive symptoms and is sensitive and specific for a diagnosis of major depressive disorder.

5. **GAD-7:** The Generalized Anxiety Disorder-7 is an 7-item valid and reliable screening instrument for four common anxiety disorders in primary care (post-traumatic stress disorder, generalized anxiety disorder, panic disorder, and social anxiety disorder). It provides a continuous measure of anxiety symptoms.

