#### Description of the Intervention

**Overview:** The intervention is

Veteran-centered, multidisciplinary, addresses palliative and psychosocial issues, and integrates with PCP care (**Table 4**). A nurse ([name]) and a social worker (Master's level, e.g., MSW) will be the primary intervention personnel. The nurse and social worker will meet weekly for approximately 60 minutes with a collaborative care team ("Team") including a representative PCP and palliative care specialist. Each site (VA ECHCS, PSVAHCS) will have a Team. The Team will provide caseload supervision and write notes and orders for patient's clinical providers to sign.

**Team collaborative care model:** The Team will provide symptom-based care by integrating palliative symptom management with CHF, ILD, and/or COPD disease-specific care plans based on the intervention team interviews/evaluations of patients and medical record review. Study staff will record the Team's recommendations in a progress note in the Veteran's electronic medical record. The psychosocial care and other non-pharmacological recommendations (e.g., pacing) will be implemented immediately by the intervention team. Orders for medications or tests will be written for patient's clinical providers to review & sign at their discretion. This integration into ongoing primary care both informs patient's clinical providers of the intervention care plan and provides an extra level of safety for patients by asking clinical providers to sign medical orders. The team will have phone access to a cardiologist and pulmonologist for specialist support and will re-review patients if their symptoms are not improving as assessed by the study staff.

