**Control Group (treatment as usual plus information from baseline surveys and self-care materials)**

Patients in the control group will continue to receive care at the discretion of their providers, which may include referrals to and ongoing care from cardiology, pulmonary, palliative care, or mental health. They will also have the same amount of interaction with research assistants as the intervention patients, completing questionnaires and participating in study visits at the same frequency. Patients' providers will be given the results of all baseline depression surveys if screen positive for depression. For example, patients in the usual care arm who have significant depressive symptoms will be notified of this and their providers will also be contacted. Referring providers will then assume responsibility for depression care at their discretion, with no constraints on treatment or referrals. Therefore, the usual care patients may benefit from self-care materials or the feedback of screening instruments to their referring providers. This sets a high but appropriate standard by which to judge the effectiveness of the intervention. We considered a control group that included time with a nurse or social worker to match the intervention patients' time ("attention control"). However, this is not feasible as the intervention "dose" of nursing and social work care varies according to patient needs and symptoms. It would not be possible to match the "dose" of provider time in both groups.

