**D. Description, Risks and Justification of Procedures and Data Collection Tools:**

**Aim 1:** Study personnel will administer measures four times: enrollment (baseline), 4 months, 6 months and 12 months (**Table 5**). The baseline and 6-month measures which are comprised of approximately 120 questions and are expected to last 45 minutes, will be obtained during an in-person visit, by mail and phone or by video teleconference. We will allow patients to complete 4 month and 12 month measures by mail or phone if they prefer. Veterans will be offered an incentive for completing each of the 4 study visits (\$10 at baseline, \$10 at 4 months, \$15 at 6 months, \$10 at 12 months). Patient reported survey data is necessary to achieve study aims as the primary outcome is quality of life which is patient perceived. Demographic data and information from medical record review is necessary to determine secondary outcomes. We have implemented the following protections:

Table 5. Study Visits and Assessments	Baseline	Month 4	Month 6	Month 12
Demographics/study form	X			
FACT-G (primary outcome)	X	X	X	X
PHQ-8, GAD-7	X	X	X	
KCCQ-12, CCQ, K-BILD	X	X	X	
QUAL-E, Symptom Assessment, GSDS	X		X	
Advance care planning communication, assess for advance directive documentation	X		X	
Medications	X		X	
Health care utilization, vital status, risk of hospitalization/death			X	X
Use of other medical services	X		X	

Satisfaction	X	X
--------------	---	---

Medical record data will be gathered for up to ten years after each participant concludes active study participation. The purpose of this is to determine the effect of the intervention on long-term health and health care use. This could include but is not limited to hospital discharge summaries, progress notes, operative notes, laboratory results, and diagnostic tests.

Protection against loss of confidentiality.

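### The protocol does not stop the nurse and social worker who deliver the intervention from also collecting the self-reported 6-month FACT-G, although research staff appear to be the usual collectors

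*Protocol*

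**What the plan says.** **Who may act.** Protocol section IV.C, Recruitment Process (Aim 1), names the research coordinator and research assistant, and adds that the "study social worker and the study nurse may contact and conduct study procedures with patients according to the protocol at both sites". Outcome assessment is not excepted.

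**Who treats.** Section IV.C, Description of the Intervention, says that a nurse "and a social worker (Master's level, e.g., MSW) will be the primary intervention personnel". Each makes about six visits per patient, two a month. The last paragraph of section II adds: "The Intervention SW and RN at each site will interact with participants at both sites".

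**Who collects outcomes.** Section IV.D, Aim 1: "Study personnel will administer measures four times: enrollment (baseline), 4 months, 6 months and 12 months". The baseline and 6-month measures "will be obtained during an in-person visit, by mail and phone or by video teleconference"; the 4- and 12-month measures may be done by mail or phone.

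**What points to research staff.** Section IV.C, Control Group, says of control patients: "They will also have the same amount of interaction with research assistants as the intervention patients, completing questionnaires and participating in study visits". It adds that the two arms do not differ in how often this happens. The last paragraph of section II has Colorado research staff helping Puget Sound with some follow-up data collection, and mentions the intervention nurse and social worker separately.

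**The outcome.** Section IV.A describes the FACT-G as a "responsive 27 item self-report measure of health-related quality of life". It is the sole primary outcome, assessed at 6 months in both the protocol and the SAP.

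**The concern.** The FACT-G is subjective, patients know their arm, and section IV.C explains why an attention control was rejected. Keeping outcome collection apart from treatment is one of the few protections left. Self-completion does not remove the interviewer, because personnel administer the measures and may do so in person, by phone or by video.

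A patient who answers quality-of-life questions to a nurse or counsellor after months of contact may answer more favourably. Only intervention patients have such a relationship, so the shift would favour the intervention and could not be told apart from a treatment effect. The same applies to the other self-reported measures, such as PHQ-8, GAD-7 and QUAL-E. The planned mixed models and pattern mixture analyses deal with missing data and would not reveal it.

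**Working it through.** **Reading the text.** Three steps are needed for the exposure to exist.

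1. The nurse and social worker may conduct study procedures: stated in Recruitment Process.
2. Administering the measures is a study procedure given to study personnel: stated in section IV.D. Section IV.D also uses study personnel for staff who telephone participants generally, and section IV.E says most of the intervention is delivered by phone. The term therefore does not exclude intervention staff.
3. Nothing elsewhere withdraws the permission. The protocol text on randomization, training and quality assurance, data quality, monitoring and analysis contains no masked collection, no separation of roles and no record of who collected a measure. Nor does the SAP.

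**Inputs for scale.** From Sample Size (section IV.C): SD 15, design effect 0.4 SD = 6 points, minimal important difference 4-6 points, two-sided alpha 0.05, about 115 completers per arm. The same section's 5% deaths and 15-20% missing data would leave 400 × 0.75 / 2 = 150 to 400 × 0.80 / 2 = 160 per arm, so I use 115 to 160. Section IV.F expects a baseline correlation above 0.5; I use r from 0 to 0.5.

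**The plan's own figure.** SE = 15 × sqrt(2/115) = 1.98. Power = Φ(6/1.98 − 1.96) = Φ(1.07) = 0.858, or 0.856 with the t distribution. The stated 85% is reproduced.

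**Effect of a one-sided shift.** Let s be the reporting shift in an affected assessment and p the share of intervention-arm assessments affected. Both are assumptions. The between-arm bias is b = p × s. With no true effect, the rejection probability is P(|Z + b/SE| > 1.96), where SE = 15 × sqrt(1 − r²) × sqrt(2/n).

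- n = 115, r = 0: SE = 1.98
- n = 160, r = 0.5: SE = 15 × 0.866 × 0.1118 = 1.45

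With s = 2 points:

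| Share affected | b (points) | Error, SE 1.98 | Error, SE 1.45 |
|---|---|---|---|
| All | 2.0 | 17.3% | 28.0% |
| Half | 1.0 | 8.0% | 10.6% |
| Quarter | 0.5 | 5.7% | 6.4% |

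As an example, for the quarter share at SE 1.98: b/SE = 0.253, and P(Z > 1.707) + P(Z < −2.213) = 0.044 + 0.013 = 0.057. A full 2-point bias is one third of the 6-point design effect and lies below the minimal important difference.

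**The case against.** The permission sits in the recruitment section, next to text on referral and on training in screening and consent. It may be meant only to say who can work across sites, and it is limited to acting as the protocol provides. No passage assigns outcome measures to the nurse or social worker. The Control Group text links questionnaires to research-assistant contact that is equal in the two arms, and section II gives cross-site follow-up help to research staff. A study protocol manual with data-collection instructions is mentioned under Data management but is not among the documents, and it may already separate the roles.

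Most of this stands. It makes research staff the likely usual collectors. A reader might infer that intervention patients will report to their own therapist while controls report to a stranger. The documents do not support that, and it would conflict with the equal-contact statement. What remains is that these passages describe the usual arrangement without reserving the task, while the permission is express and has no exception for outcomes.

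Two further points are fair. Mail completion limits interviewer influence. Full masking may also be hard: section IV.F makes the research assistant a primary coder of Aim 2a data, which include interviews with intervention patients, so that person could learn allocation.

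**Conclusion.** The concern holds as a gap in the protocol, not as evidence that bias will occur. The text allows intervention staff to collect the 6-month FACT-G and contains no rule on separation or masking. How often this would happen is unknown.

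The size is conditional. For an assumed 2-point shift, the two-sided error is about 17-28% if every intervention-arm assessment is affected and about 6% if a quarter are. A reader might take the higher figures as a forecast. They are not: they require intervention staff to collect essentially all intervention-arm outcomes, which the passages on research assistants make unlikely. The figures also assume that control responses are unaffected and that the SD is unchanged. The change is worth making because it is cheap and protects a subjective sole primary outcome.

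**What to change.** In Recruitment Process (IV.C) and in section IV.D, Aim 1, state that the 4-, 6- and 12-month measures are collected only by research staff who do not deliver the intervention. Where a site has no suitable collector, use the cross-site follow-up support described at the end of section II.

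Mask collectors to arm where feasible. For example, do not give a participant's later follow-up to a staff member who has handled that participant's Aim 2a interview. Those interviews come after the 6-month measures, so this step mainly protects the 12-month assessment.

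Record collector and mode for each assessment, and report by arm any collection by intervention or unmasked staff. Add to the SAP a sensitivity analysis by collector or mode, for example refitting the primary model with FACT-G scores collected by intervention staff set to missing. If collection has finished, the reporting and sensitivity analysis remain possible wherever the collector was recorded.

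The cost is a few sentences of text, two recorded fields, less scheduling flexibility and some splitting of duties. Separating roles implies no new staff, since research assistants already take part in study visits; masking is not shown to be equally cheap. Sample size and power do not change. Patients' own expectation bias remains, because they know their arm.

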#### Randomization - Aim 1:

Randomization will occur at the patient level with 1:1 randomization of patients to intervention or control groups. Randomization will be computer generated using random block sizes and stratified by site and disease CHF, ILD, or COPD, or both CHF and COPD.

#### Sample Size

The sample size was planned to detect a clinically significant change on the primary outcome, quality of life. We plan to enroll 400 Veterans and anticipate 5% will die and 15-20% will have missing outcome data because they did not complete surveys or dropped out. Thus approximately 115 Veterans per arm will complete the study. With this sample size, we will have 85% power to detect a moderate effect size of 0.4 (two-sided test, alpha=0.05). The minimal clinically important difference on the FACT-G is 4-6 points, and with a standard deviation of 15, a Cohen's d effect size of 0.4 will be on the high end of clinical significance. We believe this is appropriate as this is a personnel-intensive intervention. **Table 3** illustrates a range of sample sizes per study arm with different power and effect size assumptions.

**Table 3. Sample sizes per study arm for different assumptions**

Effect size	Power		
	80%	85%	90%
0.35	130	148	173
0.40	100	114	133
0.45	79	90	105

#### **Aim 2a:**

*Patient interviews:* Patients will consent to participate in interviews when they provide informed consent for Aim 1.

*Intervention personnel:* All intervention personnel will be asked to participate in the focused group discussion. Recruitment and consent: Those who agree will be asked to provide verbal consent to the following at the beginning of all focus group:

- Full disclosure that the session will be digitally recorded and detailed notes taken;
- Statement that responses will be kept confidential and names will not be linked with responses in the summary;
- An opportunity for them to excuse themselves

*Primary care providers whose patients have received the intervention:* Providers will be invited to complete the survey via email, phone or in-person. By completing in the survey, they will provide consent for this portion of the study. We will request a waiver of written consent for providers who complete the survey because the surveys are minimal risk, and it is impractical to obtain written consent from busy health care providers.

#### Description of the Intervention

**Overview:** The intervention is

Veteran-centered, multidisciplinary, addresses palliative and psychosocial issues, and integrates with PCP care (**Table 4**). A nurse ([name]) and a social worker (Master's level, e.g., MSW) will be the primary intervention personnel. The nurse and social worker will meet weekly for approximately 60 minutes with a collaborative care team ("Team") including a representative PCP and palliative care specialist. Each site (VA ECHCS, PSVAHCS) will have a Team. The Team will provide caseload supervision and write notes and orders for patient's clinical providers to sign.

**Team collaborative care model:** The Team will provide symptom-based care by integrating palliative symptom management with CHF, ILD, and/or COPD disease-specific care plans based on the intervention team interviews/evaluations of patients and medical record review. Study staff will record the Team's recommendations in a progress note in the Veteran's electronic medical record. The psychosocial care and other non-pharmacological recommendations (e.g., pacing) will be implemented immediately by the intervention team. Orders for medications or tests will be written for patient's clinical providers to review & sign at their discretion. This integration into ongoing primary care both informs patient's clinical providers of the intervention care plan and provides an extra level of safety for patients by asking clinical providers to sign medical orders. The team will have phone access to a cardiologist and pulmonologist for specialist support and will re-review patients if their symptoms are not improving as assessed by the study staff.

**Structured psychosocial care:** The social worker will conduct a psychosocial assessment, and provide 6 phone-based counseling sessions. This counseling was specifically developed and tested in patients with CHF or COPD to improve depression (see Preliminary Studies). The purpose is to help veterans adjust to living

**Table 4. Intervention Overview**

Intervention Component	Personnel
Algorithm-guided symptom management: breathlessness, fatigue, pain, trouble sleeping	Registered Nurse (RN)
Structured psychosocial care, targeting depression and adjustment to illness; advance care planning	Social Worker
Team collaborative care model: 30-60 minute weekly team meetings	RN, LCSW, palliative and primary care providers

with CHF, ILD, or COPD and to activate/empower them to discuss issues related to their illness with their care providers. The counseling will be supplemented with antidepressant medication if the Team agrees providing antidepressant medication is an appropriate, evidenced-based recommendation. The social worker will also follow up on the patient-completed advance care planning preference form to help patients clarify health care goals and complete written advance directives. The nurse will assist the social worker as needed for this part of the intervention.

**Advance Care Planning:** The intervention team will meet with the patient one time to discuss care goals. Using a structured guideline, participants understanding of their illness will be assessed. Questions about what is important, goals, concerns and fears will be asked. If a caregiver is present, s/he will be invited to participate in the discussion. The discussion will be documented in the medical record.

**Control Group (treatment as usual plus information from baseline surveys and self-care materials)**

Patients in the control group will continue to receive care at the discretion of their providers, which may include referrals to and ongoing care from cardiology, pulmonary, palliative care, or mental health. They will also have the same amount of interaction with research assistants as the intervention patients, completing questionnaires and participating in study visits at the same frequency. Patients' providers will be given the results of all baseline depression surveys if screen positive for depression. For example, patients in the usual care arm who have significant depressive symptoms will be notified of this and their providers will also be contacted. Referring providers will then assume responsibility for depression care at their discretion, with no constraints on treatment or referrals. Therefore, the usual care patients may benefit from self-care materials or the feedback of screening instruments to their referring providers. This sets a high but appropriate standard by which to judge the effectiveness of the intervention. We considered a control group that included time with a nurse or social worker to match the intervention patients' time ("attention control"). However, this is not feasible as the intervention "dose" of nursing and social work care varies according to patient needs and symptoms. It would not be possible to match the "dose" of provider time in both groups.

